8.4.3.3. Additional Procedural Data

- Total procedure time, PVI time, PFA application time, mapping time, and PFA application time per lesion
- Total Fluoroscopy Time
- Ablation parameters per application
- Device(s) utilized (per ablation)

8.5 Analysis of Primary Endpoint(s)

8.5.1 Analysis of Primary Safety Endpoint

In the Pilot phase and the Pivotal roll-in phase, the primary safety endpoint will be summarized descriptively using the total number of PAEs, the number of subjects who experience PAEs, and the percentage of subjects who experience PAEs. The SA will be used to analyze the PAE data from the Pilot phase, while the Roll-In analysis set will be used to analyze the safety data from the Pivotal roll-in phase.

In the Pivotal main phase, hypothesis testing will be performed in the mITT analysis set. Subjects with non-missing PAE outcome data will be included in the primary analysis. The primary safety endpoint will be evaluated using the exact test for a binomial proportion at a one-sided significance level of 2.5%. If the upper bound of the exact two-sided 95% confidence interval of the primary safety endpoint rate is less than the performance goal of 12%, the study will be considered to have demonstrated safety.

To investigate the robustness of the analysis result, sensitivity analyses including estimation of the PAE rate in the SA, worst-case and best-case scenario analyses, and tipping point analysis will be performed in the SA and mITT analysis sets. Details are provided in Section 8.6.

8.5.2 Analysis of Primary Effectiveness Endpoint

In the Pilot phase and the Pivotal roll-in phase, the primary effectiveness endpoint will be summarized descriptively as the number and percentage of subjects free from primary effectiveness failure. The SA will be used to analyze the primary effectiveness endpoint data from the Pilot phase and the Roll-In analysis set will be used to analyze the data from the Pivotal roll-in phase.

In the Pivotal main phase, hypothesis testing will be performed in the PP analysis set. Subjects with non-missing primary effectiveness endpoint (PEE) outcome data will be included in the primary

analysis. The primary effectiveness endpoint will be evaluated using the exact test for a binomial proportion at one-sided significance level of 2.5%. If the lower bound of the exact two-sided 95% confidence interval of the primary effectiveness success rate is greater than the performance goal of 50%, the study will be considered to have demonstrated effectiveness.

[REDACTED]

[REDACTED]

[REDACTED]

[REDACTED]

[REDACTED]

[REDACTED]

[REDACTED]

[REDACTED]

To investigate the robustness of the analysis result, sensitivity analyses including estimation of the primary effectiveness success rate in the mITT and All Treated analysis sets, worst-case and best-case scenario analyses, tipping point analysis, and Kaplan-Meier estimation will be performed in the PP, All Treated, and mITT analysis sets. Details are provided in Section 8.6.

8.5.3 Criteria for Study Success

The study will be considered a success if both primary safety and effectiveness endpoints are met.

8.6 Sensitivity Analyses

8.6.1 Primary Safety Endpoint

The following sensitivity analyses will be performed in the Pivotal main study SA and mITT analysis sets unless otherwise specified:

- **Sensitivity to Analysis Set**

[REDACTED]

- **Best-case Scenario**

[REDACTED]

[REDACTED]

[REDACTED]

[REDACTED]

- **Worst-case Scenario**
[REDACTED]
[REDACTED]
[REDACTED]

- **Tipping Point Analysis**
[REDACTED]
[REDACTED]
[REDACTED]
[REDACTED]
[REDACTED]
[REDACTED]

8.6.2 Primary Effectiveness Endpoint

The following sensitivity analyses will be performed in the Pivotal main study mITT, All Treated, and PP analysis sets unless otherwise specified:

- **Sensitivity to Analysis Set**
[REDACTED]
[REDACTED]

- **Kaplan-Meier Analysis**
[REDACTED]
[REDACTED]
[REDACTED]
[REDACTED]
[REDACTED]
[REDACTED]

- **Best-case Scenario**
[REDACTED]
[REDACTED]
[REDACTED]
[REDACTED]
[REDACTED]

- **Worst-case Scenario**

[REDACTED]

[REDACTED]

[REDACTED]

[REDACTED]

- **Tipping Point Analysis**

[REDACTED]

[REDACTED]

[REDACTED]

[REDACTED]

[REDACTED]

[REDACTED]

[REDACTED]

[REDACTED]

8.7 Subgroup Analyses

In order to provide additional characterization and interpretation of the primary effectiveness and safety outcomes, the below specified subgroup analyses will be performed in the Pivotal main phase.

[REDACTED]

- **Baseline Characteristics:**

- Age group: <65 vs. \geq 65 years
- CHA₂DS₂-VASC Score: \leq 2 vs. >2
- Race

- **Sex:** [REDACTED]

[REDACTED]

- **Operator Experience:** [REDACTED]

8.8 Assessment of Site Homogeneity

There will be up to 40 US sites recruiting approximately 225 evaluable subjects in the Pivotal main phase of the study. Each site should enroll no more than 15% of the total enrollment to minimize the possibility that the study results are highly influenced by a few sites. In order to assess the assumption of clinical comparability and justify pooling of the primary outcome data, homogeneity across individual sites for the primary safety and effectiveness endpoints will be examined both descriptively and formally for subjects in the Pivotal main phase.

A horizontal bar composed of five thick black lines of varying lengths, with the shortest line at the bottom.

8.9 Exploratory Analyses

A series of horizontal black bars of varying lengths, decreasing in size from top to bottom. The bars are evenly spaced and extend across the width of the frame.

A series of nine horizontal black bars of varying lengths, decreasing in length from top to bottom. The bars are evenly spaced and extend across the width of the frame.

8.10 Handling of Missing Data

Missing data will be queried for reasons and handled on an individual basis.

- Primary Safety Endpoint: [REDACTED]

- **Primary Effectiveness Endpoint:**

8.11 Adjustments for Multiplicity

For the Pivotal main phase, the Type I error for each of the primary endpoints is controlled at a one-sided 2.5% level. The secondary endpoint will only be tested if the primary endpoints are met. The Family-wise error rate for the primary and secondary hypothesis tests will be controlled at a level of 2.5% by using this gatekeeping strategy. [REDACTED]

8.12 Analyses of Secondary Endpoints

Baseline AFEQT scores and changes from baseline at each follow-up timepoint the questionnaire is administered will be summarized descriptively in the Pilot SA, Pivotal main phase mITT and PP, and the Pivotal Roll-In analysis sets for the following five scores. ■

If both primary endpoints are met, then hypothesis testing will be performed in the Pivotal main phase PP analysis set. A paired t-test at an alpha level of 2.5% will be used to test the mean change of overall AFEQT scores between baseline and 12 months post ablation procedure. If the mean change of the overall AFEQT score is greater than 0 and the statistical test p-value is ≤ 0.025 , then the null hypothesis will be rejected in favor of the alternative hypothesis of AFEQT improvement.

8.13 Additional Endpoint Analyses

No formal statistical hypotheses will be formulated or performed for the additional endpoints. Descriptive statistics will be provided on all additional endpoints in the analysis sets specified below.

8.13.1 Additional Safety Endpoints

The additional safety endpoints will be summarized descriptively as the total number of events, the number of subjects with events, and the percentage of subjects with events and will be conducted in the Pilot SA, Pivotal main study SA, and Pivotal Roll-In analysis sets.

8.13.2 Additional Effectiveness Endpoints

The additional effectiveness endpoints will be summarized descriptively as described below and will be conducted in the Pilot SA, Pivotal main study mITT and PP, and Pivotal Roll-In analysis sets.

- **Acute procedural success:** The number and percentage of subjects and clinically relevant targeted PVs with acute procedural success will be presented.
- **Acute reconnection:** The number and percentage subjects and clinically relevant targeted PVs where acute reconnection was identified by adenosine/isoproterenol challenge will be presented:

[REDACTED]

[REDACTED]

[REDACTED]

- **FPI:** The number and percentage of subjects and clinically relevant targeted PVs with achievement of entrance block after first encirclement evaluated prior to the adenosine challenge:

■ [REDACTED]
■ [REDACTED]
■ [REDACTED]
■ [REDACTED]

- **Touch-up by NSC:** The number and percentage of subjects and clinically relevant targeted PVs ablated by a NSC to achieve PVI:

■ [REDACTED]
■ [REDACTED]
■ [REDACTED]
■ [REDACTED]

- **Repeat ablation procedure:**

- **Occurrence of repeat procedures:** Kaplan-Meier estimates and plots will be used to characterize the time to the first repeat ablation procedure for AF/AT/AFL of unknown origin. The proportion of subjects who are free from repeat ablation for AF/AT/AFL of unknown origin at each monthly timepoint post index procedure will be presented.

[REDACTED]
[REDACTED]
[REDACTED]
[REDACTED]

- **PV reconnection:** The number and percentage of subjects and PVs and at the repeat procedure where PV reconnection was observed:

■ [REDACTED]

- **Freedom from documented (symptomatic and asymptomatic) atrial tachyarrhythmia off Class I/III AAD:** Kaplan-Meier estimates and plots will be used to characterize the time to first documented (symptomatic and asymptomatic) atrial tachyarrhythmia episodes based on electrocardiographic data (≥ 30 seconds on ECG or sponsor provided CEM or Holter device) during the effectiveness evaluation period (Day 91-Day 365). Taking any Class I/III AAD for AF/AT/AFL of unknown origin during the evaluation period will also be deemed a failure. The proportion of subjects who are free from failure at each monthly time point post blanking will be presented.
- **12 Month Single Procedure Treatment Success:** Kaplan-Meier estimates and plots will be used to characterize the time to first documented symptomatic atrial tachyarrhythmia episodes based on electrocardiographic data (≥ 30 seconds on ECG or sponsor provided CEM or Holter device) during the effectiveness evaluation period (Day 91-Day 365) following a single index ablation procedure with all other failure modes included. The proportion of subjects who are free from failure at each monthly time point post blanking will be presented.
- **Clinical Success:** Kaplan-Meier estimates and plots will be used to characterize the time to first documented symptomatic atrial tachyarrhythmia episodes based on electrocardiographic data (≥ 30 seconds on ECG or sponsor provided CEM or Holter device) during the effectiveness evaluation period (Day 91-Day 365). The proportion of subjects who are free from failure at each monthly time point post blanking will be presented.
- **CCS-SAF:** Baseline CCS-SAF scores and the mean change from baseline at each follow-up timepoint the questionnaire is administered will be summarized descriptively. [REDACTED]
[REDACTED]
[REDACTED]
- **Reduction in CV Hospitalization:** Baseline and follow-up rates for the time intervals 0-6 months and >6-12 months will be summarized descriptively. [REDACTED]
[REDACTED]

- **Reduction in DCCV:** Baseline and follow-up rates for the time intervals 0-6 months and >6-12 months will be summarized descriptively. [REDACTED]
- **AAD Utilization by Timing:** Baseline and follow-up AAD usage will be summarized descriptively. [REDACTED]
[REDACTED]
[REDACTED]
[REDACTED]
[REDACTED]
[REDACTED]
[REDACTED] Separate summaries will be presented for all AADs and Class I/III AADs.

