9.2.4.2 Effectiveness Endpoints

The following additional effectiveness endpoints will be assessed:

- Acute procedural success, defined as the percent of subjects with electrical isolation of all PVs with confirmed entrance block at the end of the procedure.
 - Acute reconnection identified by adenosine/isoproterenol challenge.
 - First pass isolation (achievement of entrance block after first encirclement evaluated prior to the 30-min waiting period and adenosine challenge)
 - Ablation by a non-study catheter for PVI (touch-up) among all clinically relevant targeted PVs and by subject
- Repeat ablation procedures
 - Timing (blanking period or after blanking)
 - % PV reconnection by targeted PV and by subject
 - Arrhythmia treated or non-PV targets
- Freedom from documented (symptomatic and asymptomatic) atrial tachyarrhythmia episodes based on electrocardiographic data (≥ 30 seconds on ECG or sponsor provided TTM or Holter device) during the effectiveness evaluation period (Day 91-Day 365) with the following criteria also deemed failure:
 - Taking any AAD (Class I or III) for AF beyond the 3-month follow-up visit window (i.e., at any time from day 105-365 post index procedure).
- 12 Month Single Procedure Treatment Success off AAD: The 12-month single procedure success is defined as freedom from documented symptomatic AF/AT/AFL (of unknown origin⁺) episodes based on electrocardiographic data (≥ 30 seconds on ECG or sponsor provided TTM or Holter device) through the effectiveness evaluation period following a single index ablation procedure with all other failure modes included:
 - Acute procedural failure
 - Non-study catheter failure, including:
 - use of a non-study catheter (NSC) to treat pulmonary vein targets/isolation of clinically relevant PVs (all PVs except those that are silent and/or cannot be cannulated) and left atrial non-PV AF targets during the index procedure.
 - AAD failure: Taking a new AAD (Class I & III) for atrial tachyarrhythmia (AF, AT or AFL of unknown origin⁺) or taking a previously failed Class I/III AAD, at a greater than the highest ineffective historical dose, for AF/AFL/AT beyond the 3-month follow-up visit window (i.e., at any time from day 105-365 post index procedure).

- Any DC cardioversion procedure during the evaluation period for documented atrial tachyarrhythmia (AF, AT or AFL of unknown origin[†]) recurrences ascertained through protocol specified arrhythmia monitoring methods (12-lead ECG, TTM and Holter).

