13.5 Post Procedure Follow-Up Assessments

The subjects will be required to complete follow up visits through 12 months (365 days) post initial ablation procedure. Follow-up schedules will be based on a 30-day month.

Follow-up visits should be scheduled according to the following timeframes: 7 day +3 days (7D, day 7-10), 1 month \pm 7 days (1M, day 23-37), 3 month -14 days (3M, day 76-104), 6 months \pm 30 days (6M, day 150-210), and 12 month \pm 30 days (12M, day 335-395). Follow-up visit schedule will not reset if subject undergoes a repeat AF ablation procedure.

The following should be performed prior to hospital discharge:

- Physical exam including standardized neurological examination: Exam should be performed by a physician or equivalent (NP or PA). The following items will be evaluated as part of the standardized neurological examination: mental status (e.g. orientation, attention, vision, hearing, speech, level of consciousness), cranial nerve testing, assessment of gait and coordination, ability to move all extremities, and evaluation of sensory and motor strength of all 4 extremities.
- MUST be performed pre-discharge.
 - If physical exam demonstrates new abnormal neurological findings as compared to the one performed at baseline, a formal neurological consult and examination with appropriate imaging (i.e., DW-MRI) needs to be done to confirm or rule out any suspected diagnosis of stroke.
 - Diagnosis of stroke/CVA must be confirmed by at least one of the following:
 - Neurology or neurosurgical specialist
 - Neuroimaging procedure (MR or CT scan or cerebral angiography)
 - Lumbar puncture (i.e., spinal fluid analysis diagnostic of intracranial hemorrhage)
 - Stroke: (diagnosis as above, preferably with positive neuroimaging study)
 - Minor—Modified Rankin score <2 at 30 and 90 days
 - Major—Modified Rankin score \geq 2 at 30 and 90 days
 - MRS assessments should be made by certified individuals
- AFL/AT/AF recurrence
- Electrocardiogram (12-Lead ECG)
- Transthoracic Echocardiogram (TTE), for evaluation pericardium for possible pericardial effusion and/or pericarditis. In the event significant pericardial effusion is identified, subjects should be followed until the condition resolves.

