[REDACTED] The Pivotal main phase will enroll 248 subjects (225 evaluable subjects plus 10% attrition). Data for roll-in subjects will be analyzed separately from the main phase and will not be counted towards the enrollment cap of 225 evaluable subjects of the Pivotal main phase.

After the study ablation procedure, subjects will be followed up for 12 months, including a 3-month blanking period (Day 0-90) and followed by a 9-month evaluation period (Day 91-365). All subjects will be evaluated at 7 days, 1, 3, 6, and 12 months following the index procedure. There will be no formal interim analysis (sample size analysis or early success analysis) in this study.

2 Treatment Assignment

All subjects will be treated with the IRE Ablation System, which includes the multichannel generator (TRUPULSE™) and circular multielectrode catheter (VARIPULSE™).

3 Randomization and Blinding Procedures

This is a single-arm non-randomized trial with all subjects undergoing ablation procedure with the IRE ablation system. Therefore, masking of treatment assignment for operators and subjects is not applicable.

This study will employ several measures to minimize operational bias:

- Screening logs will be maintained at sites to confirm eligible subjects are considered for participation in the study.
- Sponsor personnel directly involved in the conduct of the study will not have access to intermediate aggregated summaries of primary safety and effectiveness endpoint data (from the Pivotal main phase) until preparation for filing for approval.

4 Interval Windows

Subjects will undergo a 3-month blanking period (Day 0-90) followed by a 9-month evaluation period (Day 91-365) and will be scheduled for evaluation at 7 days, 1, 3, 6, and 12 months following the index procedure per the table below. Discontinued subjects who had the study catheter inserted but do not undergo PFA delivery will remain in follow-up for safety for 3 months post catheter insertion and then will be discontinued from the study. All study intervals are calculated from the date of the index procedure (Day 0). Details of the pre- and post-procedure scheduled assessment are provided in the protocol.

Visit	Pre-Procedure	Ablation/Discharge		Phone/Virtual	Follow-Up Visits			
	Screening/Baseline	Study Index Procedure Day 0	Discharge	7D (D7-10)	1M (D23-37)	3M (D76-104)	6M (D150-210)	12M (D335-395)
Visit no.	1	2	3	4	5	6	7	8

5 Levels of Significance

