8.4.3 Additional Endpoints

No formal hypothesis testing will be performed for additional endpoints.

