8.4.3.2. Additional Effectiveness Endpoints

- **Acute procedural success:** Defined as the achievement of electrical isolation in all clinically relevant targeted PVs as evidenced by the confirmation of entrance block at the end of the index procedure. Use of a non-study catheter to achieve pulmonary vein isolation (PVI) due to an IRE-system malfunction is considered an acute procedural failure.
- **Acute reconnection:** Defined as the restoration of electrical conduction in any clinically relevant targeted PV as identified by adenosine/isoproterenol challenge during the index procedure.
- **First pass isolation (FPI):** Defined as the achievement of entrance block in all clinically relevant targeted PVs after first encirclement, evaluated prior to the adenosine challenge during the index procedure.
- **Touch-up by NSC:** Defined as the use of a NSC to achieve PVI in any clinically relevant targeted PV during the index procedure.

- **Repeat ablation procedures** for AF/AT/AFL of unknown origin during the 12-month follow-up period will be assessed. The evaluation will include the timing of repeat ablation (blanking period or evaluation period), any reconnections of PVs previously isolated during the index procedure, and the type of arrhythmia(s) treated during the repeat ablation, along with their corresponding targets.
- **Freedom from documented (symptomatic and asymptomatic) atrial tachyarrhythmia off Class I/III AAD:** Defined as freedom from documented (symptomatic and asymptomatic) atrial tachyarrhythmia episodes based on electrocardiographic data (≥ 30 seconds on ECG or sponsor provided CEM or Holter device) during the effectiveness evaluation period (Day 91-Day 365). Taking any Class I/III AAD for AF/AT/AFL of unknown origin beyond the 3-month visit window (i.e., any time from Day 105-365 post index procedure) will also be deemed a failure.
- **12 Month Single Procedure Treatment Success:** Defined as freedom from documented symptomatic atrial tachyarrhythmia episodes based on electrocardiographic data (≥ 30 seconds on ECG or sponsor provided CEM or Holter device) during the effectiveness evaluation period (Day 91-Day 365) following a single index ablation procedure with all other failure modes included.

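### The SAP gives two antiarrhythmic-drug failure windows (Day 105-365 and Day 91-365) for the same descriptive endpoint, freedom from atrial tachyarrhythmia off Class I/III AAD

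*SAP*

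**What the plan says.** The endpoint is defined in SAP 8.4.3.2. Class I/III AAD use for the listed arrhythmias counts as failure only "beyond the 3-month visit window (i.e., any time from Day 105-365 post index procedure) will also be deemed a failure". Protocol 9.2.4.2 uses the same days for this endpoint: "Taking any AAD (Class I or III) for AF beyond the 3-month follow-up visit window (i.e., at any time from day 105-365".

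SAP 8.13.2 sets out the Kaplan-Meier analysis of the same endpoint. There the drug rule reads: "Taking any Class I/III AAD for AF/AT/AFL of unknown origin during the evaluation period will also be deemed a failure". The sentence just before it in that bullet gives the period as Day 91 to Day 365. SAP section 4 agrees, describing a "3-month blanking period (Day 0-90) followed by a 9-month evaluation period (Day 91-365". The documents define this period in no other way.

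The endpoint is descriptive. SAP 8.4.3 states: "No formal hypothesis testing will be performed for additional endpoints".

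**The concern.** One named endpoint has two failure rules in current, unredacted SAP text. The definition tolerates drug use up to Day 104, and the analysis text tolerates it only up to Day 90. Nothing visible in the SAP says which section takes precedence, and 8.13.2 is the section an analyst would program from. Following it literally would give a result that departs from the endpoint's own definition and from the protocol.

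The gap need not be empty of subjects:

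- Protocol Table 12.1.1.1, which governs the primary endpoint, does not penalise a Class I/III drug that has been stopped by Day 104. Use in Days 91-104 is therefore foreseen.
- The 3-month visit may fall anywhere from Day 76 to Day 104. A subject seen on Day 91 or later, whose drug is stopped at that visit, lands in the gap.
- This endpoint counts any Class I/III drug taken for the arrhythmia. The primary endpoint counts only a drug new to the subject, or a previously failed one at a higher dose than before. A subject who carries on an old drug at its old dose is thus exposed to the conflict here.

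**Working it through.** The plan states no figure to reproduce. The check compares the two texts, counts days, and works out what one affected subject is worth.

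**Windows, counted inclusively**

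| Source | Failure window for AAD use | Length |
|---|---|---|
| SAP 8.4.3.2 and protocol 9.2.4.2 | Day 105-365 | 365 − 105 + 1 = 261 days |
| SAP 8.13.2, with the period from SAP section 4 | Day 91-365 | 365 − 91 + 1 = 275 days |

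The difference is 275 − 261 = 14 days (Day 91-104), or 14/275 = 5.1% of the evaluation period.

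**Classification of subjects by drug use for AF/AT/AFL**

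| Drug use | SAP 8.4.3.2 | SAP 8.13.2 |
|---|---|---|
| Ended by Day 90 | Not a drug failure | Not a drug failure |
| Some use in Days 91-104, stopped by Day 104 | Not a drug failure | Drug failure, dated within Days 91-104 |
| On drug from before Day 91 and still on it at Day 105 | Drug failure at Day 105 | Drug failure at Day 91 |
| First use on or after Day 105 | Drug failure | Drug failure, same date |

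The second row changes event status. The third row only moves the event time, by up to 14 days.

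**Effect on the tabulated estimates.** SAP 8.13.2 reports the proportion free from failure at each monthly time point after blanking. Protocol 13.5 says "Follow-up schedules will be based on a 30-day month". If the SAP's monthly points follow that convention (an assumption), the first one after Day 90 is Day 120. With calendar months it is about 4 × 365/12 = Day 122. Either falls after Day 105, so third-row subjects have failed under both rules by the first reported point, and only the plotted curve shows the shift. The difference at 12 months comes from second-row subjects with no other failure. A second-row subject who fails later for another reason differs only at the monthly points before that failure.

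**Size per affected subject, ignoring censoring**

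- Main phase, 225 planned evaluable: 1/225 = 0.44 percentage points
- Roll-in, maximum 160: 1/160 = 0.63 points
- Pilot, 20: 1/20 = 5.0 points

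**Assumed range for the main phase.** The documents do not give the number affected, so these counts are illustrations only.

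| Affected subjects (assumed) | Share of 225 | Reduction in rate |
|---|---|---|
| 5 | about 2% | 5/225 = 2.2 points |
| 11 | about 5% | 11/225 = 4.9 points |
| 23 | about 10% | 23/225 = 10.2 points |

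**The case against.** The strongest reply is that the intended rule is hardly in doubt. Section 8.4.3.2 is the definition and gives day numbers, and the protocol repeats them for this endpoint. The drug sentence in 8.13.2 gives none and reads like shorthand. The endpoint is one of many additional ones with no test, and study success rests on the two primary endpoints. Their AAD rule is Day 105-365 in both documents. Much of the SAP is redacted, including most of its general conventions, so a rule for dating drug failures may exist out of sight.

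Most of this stands as a limit on the consequences. It does not remove the conflict: the two sentences are intact and disagree, and a hidden dating convention would not make them agree. That the text points towards Day 105 is the reason to correct 8.13.2 rather than 8.4.3.2.

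Three narrower points also stand:

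- The tabulated estimates differ only if at least one subject has drug use in Days 91-104 and stops by Day 104.
- The denominator of 225 is the planned evaluable count. The endpoint is reported in the mITT and PP sets, whose definitions are redacted, so 0.44 points per subject is approximate for either.
- The protocol counts drugs taken for AF, whereas both SAP sections count drugs taken for AF, AT or AFL of unknown origin. That is a separate difference, and correcting the day window does not remove it.

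**Conclusion.** The inconsistency is real. SAP 8.13.2 opens the drug-failure window 14 days earlier than the endpoint's definition in SAP 8.4.3.2 and in protocol 9.2.4.2. Programs written from the two sections give different Kaplan-Meier results whenever subjects have drug use in the gap. Each subject who stops on Day 91-104 with no other failure moves the 12-month estimate by about 0.44 points in the main phase, more in the smaller phases. This rests on the planned sample sizes and ignores censoring. The total effect cannot be stated because the number of such subjects is not given. The 2.2 to 10.2 point range is an assumption, not a forecast.

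The consequence is confined to a descriptive endpoint. The primary and secondary tests, alpha, sample size and criteria for study success are unaffected. It should be corrected before database lock, but it does not threaten the study's conclusions.

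**What to change.** In the AAD sentence of SAP 8.13.2 for this endpoint, replace the reference to the evaluation period with Day 105 to Day 365 post index procedure, so that its day window matches SAP 8.4.3.2 and protocol 9.2.4.2. Unless redacted text already covers it, add that a drug failure in the Kaplan-Meier analysis is dated on that same window, so that a drug carried over from before Day 105 gives an event at Day 105.

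The cost is one phrase, plus one sentence if the dating rule is not already written. No new data are needed. The edit only aligns an analysis sentence with the endpoint's existing definition and says nothing about how drugs should be used.
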